Title: "Perineural Local Anesthetic Administration With a Continuous Infusion Versus Automatic Intermittent Boluses"

Primary Investigator: [name], MS (Clinical Investigation)

NTC: NCT04458467

Date: May 16, 2022

Study Protocol and Statistical Analysis Plan

Specific Aim: To determine the relationship between method of local anesthetic administration (continuous with PCA vs. intermittent dosing with PCA) for continuous peripheral nerve block and the resulting pain control.

Hypothesis: The investigators hypothesize that, compared with a traditional fixed, continuous basal infusion initiated prior to discharge, perineural local anesthetic administered with variable automated boluses at a lower dose and a 5-hour delay following discharge will (1) provide at least noninferior analgesia during the period that both techniques are functioning; and, (2) will result in a longer overall duration of administration [dual primary end points].

Enrollment: Patients 18 years and older undergoing painful foot and/or ankle surgery will be offered enrollment.

Nerve Block placement: The nerve block site will be cleaned with chlorhexidine gluconate and isopropyl alcohol (ChloraPrep One-Step, Medi-Flex Hospital Products, Inc., Overland Park, KS, USA), and a clear, sterile, fenestrated drape applied. The ultrasound probe will be readied for use and placed to visualize the short-axis (cross-section) of the target nerve. A skin wheal will be raised at the catheter-placement needle's anticipated point of entry. An 8.9 cm, 17-gauge, insulated needle (FlexTip, Arrow International, Reading, PA, USA) will be used to place all perineural catheters. The catheter-placement 17G needle will be inserted through the skin wheal, advanced in-plane beneath the US transducer and directed toward the target nerve. Normal saline (1-2 mL) will be administered via the needle to open the space around the nerve.

A flexible non-stimulating perineural catheter (FlexTip, Arrow International, Reading, PA, USA) will be inserted 2-3 cm past the needle tip. After catheter insertion, Ropivacaine 0.5% (20 mL) will be administered via the catheter under ultrasound visualization. Sensation in the tibial and peroneal nerve distributions will be checked for anesthetic effect up to 15 minutes following initial local anesthetic bolus. A "successful" regional block will be defined as sensory- and motor-block onset in all expected nerve distributions within the 15 minutes following the local anesthetic injection.

The initial local anesthetic bolus may provide complete surgical anesthesia for the procedure. Patients who desire a general anesthetic or experience a partial block that is not adequate for surgical anesthesia will receive a general anesthetic. Additional boluses of Ropivacaine 0.5% and epinephrine may be given, if needed, via the perineural catheter.

Randomization: Subjects will be randomized to one of two treatment groups: (1) automated regular boluses (ARB) with a 5-hour delay or (2) continuous infusion initiated at discharge in a 1:1 ratio using computer generated lists sealed in opaque envelopes not opened until after the nerve has been identified and deemed appropriate for catheter placement.

Postoperative Procedures: Following completion of the procedure in the operating room, an infusion pump (Infutronix, Natick, Massachusetts) with a 500 mL ropivacaine 0.2% reservoir will be attached to the patient's perineural catheter. For patients in the continuous infusion group, the pump will provide a 6 mL/h basal infusion and a 4 mL patient-controlled bolus with a 30-minute lockout (standard at UCSD). For patients in the automated intermittent bolus group, the pump will provide an automatic 8 mL bolus once every 2 hours and have a 4 mL patient-controlled bolus with a 30 minute lockout. In addition, for those in the automated intermittent bolus group, the infusion pump will be set in a "pause" mode that delays initiation of the automated bolus doses by 5 hours (this can be over-ridden by patients if they would like to initiate their perineural infusion earlier than 5 hours).

Data Collection: Data will be gathered from the patients' electronic medical record, by telephone follow-up, and from the infusion pumps memory. Subjects will be contacted via phone for the six days following surgery to collect information regarding surgical pain (Numeric Rating Scale of 0 to 10, with "0" being no pain and "10" being the worst pain ever experienced), analgesic use, number of sleep disturbances due to pain, and satisfaction with pain control.

Statistics: This study will be powered for two primary end points: (1) the average NRS queried on postoperative day 1; and (2) the duration of treatment from when the infusion pump was initially turned on until the local anesthetic reservoir was exhausted. The dual hypotheses will be tested with a serial testing strategy, such that Hypothesis 2 will not be formally tested unless the conclusion of Hypothesis 1 is at least "noninferiority". Noninferiority will be assessed by comparing the lower limit of the 95% confidence interval for the difference on the NRS (range: 0 to 10) to a pre-specified noninferiority margin of 1.7 NRS units. This will provide evidence that the analgesia provided by the novel automated boluses is no worse than 1.7 NRS units compared to Continuous Basal infusion.

Baseline characteristics of the randomized groups will be summarized with means, standard deviations, and quartiles. Balance between groups will be assessed. Specifically, standardized differences will be calculated using Cohen's d whereby the difference in means or proportions is divided by the pooled standard deviation estimates. Any key variables (age, sex, height, weight, and BMI) with an absolute standardized difference >0.47 (with $1.96\sqrt{v/(2/n)}=0.47$) will be noted and included in a linear regression model to obtain an estimate of the treatment group differences adjusted for the imbalanced covariate(s). If residuals from the linear regression indicate violations of key assumptions (i.e. homoscedasticity or Gaussian distribution), data transformations and/or alternative generalized linear models will be applied as appropriate.

Secondary outcomes will also be analyzed by Wilcoxon-Mann-Whitney test, or linear models (or generalized linear models) as appropriate with covariates for any imbalanced covariates. No multiplicity adjustments will be applied for these analyses.

Sample size estimate: Power is simulated based on the distribution of pain measured with the Numeric Rating Scale (NRS) observed in previous studies. Specifically, the investigators simulate

NRS scores from a discrete distribution. This results in an expected interquartile range 1 to 4, and a median of 3 NRS units. 1000 trials were simulated in which the two groups, n=35 per group, were assumed to follow the same discrete distribution, submitted each trial to a Wilcoxon-Mann-Whitney test, and derived 95% confidence intervals. Out of the 1000 trials, 792 (79.2%) correctly resulted in a conclusion of non-inferiority; suggesting that the probability that the trial correctly concludes non-inferiority is about 80% when the groups follow exactly equivalent distributions.

If the test for Hypothesis 1 concludes noninferiority (scenario A, B, or C in Figure 1), the investigators will test for a difference in overall duration of administration again using the Wilcoxon-Mann-Whitney test.

Power is approximated by a two-sample t-test calculation. Assuming a standard deviation of SD=37 hours (corresponding to an interquartile range of 50 to 100 hours), the investigators expect that a sample size of n=35 provides 80% power to detect a mean group difference of 25 hours with a two-sided alpha of 5%.

Total enrollment: 70 subjects plus 30 for misplaced catheters or subjects otherwise unable to be randomized; and subjects who withdraw. This allows for a possible total of 100 subjects.

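### Is the start of the clock for the duration end point left open by the bolus arm's 5-hour pause?

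*Combined protocol and SAP*

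**What the plan says.** The Statistics section defines the second primary end point as "the duration of treatment from when the infusion pump was initially turned on until the local anesthetic reservoir was exhausted". The Sample size estimate section says that, once noninferiority on pain is concluded, the investigators will "test for a difference in overall duration of administration again using the Wilcoxon-Mann-Whitney test". The power statement there is "Assuming a standard deviation of SD=37 hours", with 35 per group giving "80% power to detect a mean group difference of 25 hours" at two-sided 5%.

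Postoperative Procedures describes the start of treatment: "Following completion of the procedure in the operating room, an infusion pump" with a 500 mL reservoir is connected to the catheter. The continuous arm runs at 6 mL/h. The bolus arm receives 8 mL every 2 hours, and its pump is placed in a "mode that delays initiation of the automated bolus doses by 5 hours", with the qualification that "this can be over-ridden by patients if they would like to initiate their perineural infusion earlier than 5 hours". Both arms have the same 4 mL patient-controlled bolus. Data Collection says that some data come "from the infusion pumps memory".

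The sections differ on when infusion begins. Hypothesis has the continuous infusion starting before discharge, and Randomization has it starting at discharge. Hypothesis counts the 5-hour delay from discharge, and Postoperative Procedures gives it no anchor.

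**The concern.** The pause exists in one arm only, so whether it counts moves the comparison in one direction. The Statistics section times the end point from a device event. The Hypothesis and Sample size estimate sections use a label about administration, which could be read as starting when drug first flows. Postoperative Procedures speaks of patients who override the pause as beginning their infusion, which also suggests a later start. Nobody states whether the 25 h design difference includes the pause.

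This is a primary end point tested at 5%. If the pump memory records both switch-on and first delivery (an assumption, since the plan does not say what it records), an analyst could in principle choose the start after seeing the data, and in some trials that choice would decide significance.

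**Working it through.** **Inputs.** From Sample size estimate: n = 35 per group, SD = 37 h, difference 25 h, two-sided alpha 5%. From Postoperative Procedures: reservoir 500 mL; 6 mL/h against 8/2 = 4 mL/h on average; pause of up to 5 h. Patient-controlled use is not given and is varied below as an assumption.

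**1. The plan's own figure.** An interquartile range of 50 to 100 h gives SD = 50/(2 × 0.6745) = 37.07 h. With n = 35, a difference of 25 h and SD 37, power is 80.7% by the normal approximation and 79.6% by the noncentral t. The stated 80% reproduces.

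**2. What 5 h can do at the design difference.** SE = 37 × √(2/35) = 8.84 h. The critical value t(0.975, 68 df) is 1.995, so the smallest significant observed difference is 17.65 h. With a full 5 h pause in every bolus patient, an observed delivery difference between 17.65 − 5 = 12.65 h and 17.65 h is significant on one reading only. Noncentral t power is 60.6% at 20 h, 79.6% at 25 h and 91.7% at 30 h. The readings therefore disagree in
- 79.6 − 60.6 = 19.0% of trials if the 25 h includes the pause;
- 91.7 − 79.6 = 12.1% if it does not.

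Paired simulation with the Wilcoxon-Mann-Whitney test (normal data, 20,000 trials) gives 19.6% and 12.8%. With pauses spread evenly over 0 to 5 h it gives 10.4% and 7.3%. If every patient overrides at once it is 0%. With an assumed SD of 24 h and a full pause, the t-test figures are 99.0 − 93.0 = 6.0% and 99.9 − 99.0 = 0.9%.

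**3. What the pump settings imply.** Time to empty is 500/(scheduled rate + patient-controlled rate), assuming equal patient-controlled use in both arms. Power is by noncentral t at SD 37, with the full 5 h added in the last columns.

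| Patient-controlled use (assumed) | Continuous | Bolus | Difference without / with pause | Power without / with | Readings disagree |
|---|---|---|---|---|---|
| 0 mL/h | 83.3 h | 125.0 h | 41.7 / 46.7 h | 99.6% / 99.9% | 0.3% |
| 1 mL/h | 71.4 h | 100.0 h | 28.6 / 33.6 h | 89.0% / 96.3% | 7% |
| 2 mL/h | 62.5 h | 83.3 h | 20.8 / 25.8 h | 64.1% / 82.1% | 18% |
| 4 mL/h | 50.0 h | 62.5 h | 12.5 / 17.5 h | 28.6% / 49.6% | 21% |

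The bolus arm lasts longer in every row without the pause, so the pause does not create the direction of the effect.

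**4. Which reading the text supports.** The Statistics section gives one start event and one stop event, in the same words for both arms. The start is the pump's first switch-on. Postoperative Procedures says that the pump is set to pause and that what is delayed is the automated doses. A pump must be on before it can be set to pause, and that sentence keeps the state of the pump apart from the beginning of infusion. The administration label elsewhere is shorthand for a measure that the Statistics section defines, and the definition governs.

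**The case for a change.** The strongest case for a change is that one primary end point carries two descriptions, that they differ in one arm only, and that the difference can decide the test. The scheduled-rate figure of 41.7 h assumes no patient-controlled use, whereas the plan itself is powered for 25 h. At an assumed 2 mL/h the design value lies between the two readings, at 20.8 h and 25.8 h. The loose wording on discharge could widen the gap: if both pumps are on from attachment, continuous delivery starts at once and the delay runs from discharge, the time from attachment to discharge is added. An assumed 1 to 3 h there gives up to 6 to 8 h. Writing the rule down would cost almost nothing.

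Much of this stands as fact. No sentence says that paused time counts or whether the 25 h includes it, and the arithmetic is right. The sections on when infusion starts do differ and must be reconciled; this review takes no view on which is right. What does not stand is the step to an open definition. The natural clarification would be switch-on in both arms with the pause included, which is what the Statistics section already says on its plain reading. To exploit the gap an analyst would have to depart from that wording and would need pump records that the plan does not promise. A descriptive summary from first delivery would change no conclusion, and its start would depend on patients' behaviour after randomization.

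**Conclusion.** No change to the plan is needed. The end point has a named start that is common to both arms, and followed as written it counts the pause. This is a fair comparison, because the delay is part of the randomized strategy and the hypothesis names it as such. An analyst who applies the Statistics section literally fills the gap sensibly.

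The possible effect ranges from 0% of trials (immediate override by all) through about 0.3% (full pause, scheduled rates only) to about 20% (full pause in every patient, with a true difference near or below 25 h). The upper figures rest on SD 37 h and on a pause length or patient-controlled use that the plan does not give. No stated power, sample size, test, alpha or testing order is wrong, and the expected direction does not depend on the pause. The mismatch between sections on when infusion begins is an editorial matter to be reconciled; it leaves the end point's definition as it is.

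### Does the noninferiority rule for day-1 pain leave open which arm is subtracted from which, and on which side of zero the 1.7 boundary lies?

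*Combined protocol and SAP*

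**What the plan says.** All places are in the combined protocol and SAP.

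- **Statistics, endpoint.** The first primary endpoint is "the average NRS queried on postoperative day 1".
- **Data Collection, scale.** The NRS runs from 0 (no pain) to 10 (worst pain), so a higher score is worse.
- **Statistics, rule.** "Noninferiority will be assessed by comparing the lower limit of the 95% confidence interval for the difference on the NRS", set against "a pre-specified noninferiority margin of 1.7 NRS units". The sentence names neither the arm subtracted nor the inequality, and the margin carries no sign.
- **Statistics, aim.** The following sentence says what a pass is meant to show: analgesia with automated boluses is "no worse than 1.7 NRS units compared to Continuous Basal infusion".
- **Statistics, serial testing.** "Hypothesis 2 will not be formally tested unless the conclusion of Hypothesis 1 is at least" noninferiority.
- **Sample size estimate.** In the simulation "the two groups, n=35 per group, were assumed to follow the same discrete distribution", and "Out of the 1000 trials, 792 (79.2%) correctly resulted in a conclusion of non-inferiority". The same section refers the noninferiority conclusions to scenarios A, B and C of a Figure 1. That figure is not in the text available here.

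**The concern.** This sentence is the decision threshold for a primary hypothesis, and formal testing of treatment duration depends on it. Many statisticians take differences as experimental minus control by habit. On a scale where higher is worse, that gives bolus minus continuous, and the lower limit is then the wrong end of the interval for showing that boluses are not much worse. A programmer could combine that habit with the named lower limit and contradict no written word of the rule.

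The power simulation appears to offer no protection. Both arms were drawn from one distribution, so the pass rate is the same whichever arm is subtracted, and 79.2% would not expose a reversed sign. The feared result is a trial that declares noninferiority almost regardless of how much worse boluses are.

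**Working it through.** **Inputs.** From the documents: 35 per group, margin 1.7, two-sided 95% interval, NRS quartiles 1, 3 and 4, equal arms in the simulation, and simulated power 79.2%. Assumed, because the cell probabilities are not given: an SD of 2.22 (interquartile range 3 divided by 1.349), and 2.56, the SD at which the normal formula returns 79.2%.

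**Step 1: the plan's own figure.** SE = SD × √(2/35), which is 0.531 at SD 2.22 and 0.612 at SD 2.56. With equal arms, the chance that the lower limit of continuous minus bolus exceeds -1.7 is Φ(1.7/SE - 1.96):

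- SD 2.22: Φ(3.20 - 1.96) = 0.893
- SD 2.56: Φ(2.78 - 1.96) = 0.793, by construction

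The planned method is rank-based on discrete scores, so it was also simulated. Six assumed 0 to 10 distributions with quartiles 1, 3 and 4 were used, with 4,000 trials each and Wilcoxon-Mann-Whitney intervals. Equal arms gave:

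| SD | Continuous minus bolus, lower > -1.7 | Bolus minus continuous, lower > -1.7 |
|---|---|---|
| 1.87 | 92.6% | 92.3% |
| 2.25 | 77.4% | 78.8% |
| 2.33 | 75.2% | 75.5% |
| 2.39 | 72.6% | 72.0% |
| 2.52 | 67.4% | 67.0% |
| 2.54 | 68.3% | 68.4% |

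The stated 79.2% lies inside this range. It cannot be reproduced exactly without the cell probabilities. The two columns differ only by simulation noise: near 78%, each entry has a standard error of √(0.78 × 0.22/4000) = 0.7 points.

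**Step 2: the possible readings.** Equal-arm pass rates are normal approximations at SD 2.22.

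| Reading | What a pass would show | Pass rate, equal arms |
|---|---|---|
| Continuous minus bolus, lower > -1.7 | Boluses worse by less than 1.7 | 0.893 |
| Bolus minus continuous, lower > -1.7 | Boluses better by less than 1.7 | 0.893 |
| Continuous minus bolus, lower > +1.7 | Boluses better by more than 1.7 | Φ(-3.20 - 1.96) = 1.2 × 10⁻⁷ |
| Bolus minus continuous, lower < +1.7 | Only that boluses are not proven worse by more than 1.7 | Φ(3.20 + 1.96) ≈ 1 |

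Only the first row delivers the claim in the plan's next sentence. The last two rows are also incompatible with a simulated power of 79.2%.

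**Step 3: what a reversal would cost.** Let d be the true excess pain with boluses, set at d = 1.7.

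- First row: Φ((1.7 - 1.7)/SE - 1.96) = Φ(-1.96) = 0.025 at either SD.
- Second row: Φ((1.7 + 1.7)/SE - 1.96) = Φ(6.40 - 1.96), above 0.9999 at SD 2.22, and Φ(5.56 - 1.96) = 0.9998 at SD 2.56.

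In the rank simulation at a shift of exactly 1.7, the first row passed 0.1% to 0.2% of the time and the second 99.9% to 100%. The first row falls below 2.5% because whole-number scores make the interval conservative.

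**Step 4: what the equal-arm simulation was for.** The lower limit of one difference is minus the upper limit of its reverse. With identical arms of equal size the two orders must therefore have the same pass rate. This holds for any power calculation at zero difference. It reflects the question being asked and is not a flaw in this simulation.

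**The case for a change.** The strongest case for a change is that a confirmatory rule should be readable on its own and should not have to be reconstructed from a statement of aim. The omission is real in the available text, the sentence controls both primary hypotheses, and one line would close it. A simulated scenario with boluses at least 1.7 worse would catch a reversed sign at once, as Step 3 shows.

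The drafting point stands: the formula is not written out, and writing it out would cost nothing. The rest does not make a case for change. The reconstruction is short and has one answer, since a lower limit, a scale on which higher is worse, and the stated aim fit only the first row of the table in Step 2. The reversed rule would support a different claim from the one in the adjacent sentence, so it cannot count as following the plan. The 99.9% figure presupposes a mistake in code that nobody has seen. A scenario at the margin is good practice when checking programs, but its absence does not make a power estimate wrong. Figure 1 may also show the direction, and its absence from the available text cannot be held against the plan.

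**Conclusion.** The concern does not hold as a defect. The noninferiority sentence lacks detail that any analyst can fill from the sentence after it: continuous minus bolus with the lower 95% limit above -1.7, or equivalently bolus minus continuous with the upper limit below +1.7. Applied that way, the false-pass rate at the margin is 2.5% under the normal approximation and lower with the rank method on whole-number scores. The plan's 79.2% is plausible under this rule. Power, sample size, the serial testing order and the eventual conclusion stay as they are.

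This rests on two assumptions: that the analyst honours the stated aim, and that Figure 1, not seen here, does not contradict it. The SDs and discrete distributions used above are also assumed. The choice among readings in Step 2 does not depend on them, because it follows from the scale and the stated aim.

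### The common SD of 37 h used to power Hypothesis 2 cannot hold in the continuous arm, whose reservoir is empty by 83.3 h; the 25 h difference is not tied to the pump settings either

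*Combined protocol and SAP*

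**What the plan says.** The Statistics section makes duration of treatment the second primary endpoint, measured "from when the infusion pump was initially turned on until the local anesthetic reservoir was exhausted". Hypothesis 2 is tested formally only if Hypothesis 1 ends in at least noninferiority.

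The Sample size estimate section says the investigators will "test for a difference in overall duration of administration again using the Wilcoxon-Mann-Whitney test". It then states: "Power is approximated by a two-sample t-test calculation". The inputs are one SD, not split by arm: "Assuming a standard deviation of SD=37 hours (corresponding to an interquartile range of 50 to 100 hours"). The result is that "the investigators expect that a sample size of n=35 provides 80% power to detect a mean group difference of 25 hours", at a two-sided alpha of 5%.

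The Postoperative Procedures section fixes what determines the duration. Every patient has a pump "with a 500 mL ropivacaine 0.2% reservoir will be attached" to the catheter. In the continuous arm "the pump will provide a 6 mL/h basal infusion and a 4 mL patient-controlled bolus with a 30-minute lockout". In the automated-bolus arm "the pump will provide an automatic 8 mL bolus once every 2 hours", with the same patient-controlled bolus and a 5 h initial pause that the patient can override.

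**The concern.** An endpoint that ends when a fixed volume runs out is bounded by that volume and the delivery rate. The continuous arm never runs slower than 6 mL/h, so an upper quartile of 100 h would need 6 × 100 = 600 mL, more than the pump holds. The t-test calculation needs a within-arm SD, and the one supplied cannot describe one of the two arms.

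The arms also have different limits and therefore probably different spreads. The planned test is rank-based, but its power was approximated by a t-test with a common SD. The plan's simulation covers Hypothesis 1 only.

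At stake is the power statement for a primary endpoint. The 80% and the 25 h detectable difference are figures for a distribution this trial cannot produce, so they are a poor guide to planning or to reading the result.

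**Working it through.** **Inputs.** From the Sample size estimate section: difference 25 h, SD 37 h, IQR 50 to 100 h, n = 35 per arm, two-sided 5%. From Postoperative Procedures: 500 mL reservoir; continuous arm 6 mL/h; bolus arm 8 mL per 2 h, averaging 4 mL/h; patient bolus 4 mL with a 30-minute lockout, so 0 to 8 mL/h extra in either arm; 5 h pause in the bolus arm. Patient-bolus use is not given, so the full range is carried through.

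**1. The plan's own figure.** IQR to SD under normality: 50/1.349 = 37.1 h. Exact two-sample t-test power for 25 h, SD 37 h, 35 per arm: 79.6%. The stated 80% reproduces.

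**2. Duration limits (run to exhaustion, pump-on at infusion start).**

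| Arm | Shortest | Longest | Range |
|---|---|---|---|
| Continuous | 500/(6+8) = 35.7 h | 500/6 = 83.3 h | 47.6 h |
| Automated bolus | 500/(4+8) = 41.7 h (pause overridden) | 500/4 + 5 = 130 h (pause counted) | 88.3 h |

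Discrete boluses move the 130 h by about 1 h either way.

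**3. Largest possible SD.** On a bounded range the SD cannot exceed half the range: 47.6/2 = 23.8 h (continuous) and 88.3/2 = 44.2 h (bolus). The continuous arm cannot reach 37 h. A single-peaked distribution is limited to one third of its range: 47.6/3 = 15.9 h and 88.3/3 = 29.4 h. The 37 h was derived from a normal, single-peaked shape, and under any single-peaked shape it fits neither arm.

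**4. Effect on t-test power at 25 h.** Largest root-mean-square SD: √[(23.8² + 44.2²)/2] = 35.5 h, or 35.5 × √(35/34) = 36.0 h with the n−1 divisor. Power at 36.0 h is 81.7%; at 35.5 h it is 82.8%. Smaller feasible SDs give more, for example 91.2% with SDs of 23.8 and 37 h.

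**5. Effect on the planned test at 25 h.** Wilcoxon-Mann-Whitney power was simulated with beta-shaped durations (an assumption) scaled to the limits in step 2. Over 315 single-peaked combinations, 2,000 runs each, the lowest power was 98.4%. In a second set with a similar relative spread in both arms, including shapes with mass piled at both ends, power ran from 83.6% to about 100%.

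**6. The 25 h difference.** If both arms draw patient boluses at the same average rate u (assumed), the implied difference is [500/(4+u) + 5] − 500/(6+u):

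| u (mL/h) | Bolus arm (h) | Continuous arm (h) | Difference (h) |
|---|---|---|---|
| 0 | 130.0 | 83.3 | 46.7 |
| 2 | 88.3 | 62.5 | 25.8 |
| 4 | 67.5 | 50.0 | 17.5 |
| 8 | 46.7 | 35.7 | 11.0 |

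The plan's 25 h is close to what use of 2 mL/h in both arms would produce, but no bolus use is stated. If the bolus arm drew 2 mL/h more than the continuous arm (assumed, with use varying between patients), the simulated difference was about 10 to 21 h and Wilcoxon-Mann-Whitney power about 58% to 85%.

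**7. If pump-on precedes the infusion.** An assumed gap of 4 h moves the continuous ceiling to 87.3 h and its SD limit to (87.3 − 35.7)/2 = 25.8 h; a gap of 8 h gives 91.3 h and 27.8 h. A 100 h upper quartile would need a gap of at least 100 − 83.3 = 16.7 h in a quarter of patients.

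**The case against.** The strongest reply is that this is an approximate planning assumption, labelled as an approximation, and that its error is on the safe side. That largely stands. The arithmetic is sound from its inputs, the t-test power at 25 h does not fall below about 82% for exhausted reservoirs, and plausible shapes give the planned test more than 80%. The number per arm also rests on the Hypothesis 1 simulation (79.2%).

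A second reply is that infusions may stop early, for example through dislodgement, which widens the spread. If early stops counted as durations, the continuous range would become 0 to 83.3 h and an SD up to 83.3/2 = 41.7 h would be mathematically possible. But the endpoint is defined by exhaustion, and early stops cannot lift the upper quartile to 100 h. With an assumed 20% of infusions ending early at random, simulated Wilcoxon-Mann-Whitney power was still about 87% to 96% where the difference was about 24 to 25 h.

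A reader might go further and infer that the power for Hypothesis 2 is unknown, or that the trial is underpowered for it. The documents do not support either reading. It is true that no lower bound on Wilcoxon-Mann-Whitney power holds over all shapes at a fixed mean difference, but that applies to any such test powered by a t-test and does not follow from the 83.3 h ceiling. Low power at 25 h appears only with nearly two-point bolus-arm durations: many patients pressing almost as often as the lockout allows, many almost never, and continuous-arm patients with the same button behaving nearly alike. Nothing in the plan suggests this.

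**Conclusion.** The inconsistency is real and follows from the plan's own figures. A common SD of 37 h with an upper quartile of 100 h is incompatible with a continuous arm that is empty by 83.3 h and whose SD is at most about 24 h. The stated 80% power and 25 h detectable difference are therefore not those of this trial.

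The SD error on its own appears conservative and does not undermine 35 per arm at a 25 h difference. The more sensitive input is the 25 h, which the pump settings turn into anything from about 46.7 h to 11.0 h as equal patient-bolus use goes from none to the maximum.

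This rests on three assumptions: infusions run uninterrupted to exhaustion; pump-on coincides with infusion start in the continuous arm (gaps of 4 or 8 h do not change the conclusion); and patient-bolus use lies somewhere in the range the lockout allows. The duration limits are firm under these assumptions. The simulated powers hold only for the shapes tried.

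**What to change.** Keep the endpoint, the pump settings and n. In the Sample size estimate section:

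- Replace the common SD and IQR with arm-specific durations derived from the reservoir volume and programmed rates, over a stated range of patient-bolus use that includes different use in the two arms.
- Count the 5 h pause, as the endpoint definition implies, and state any gap between pump-on and infusion start in the continuous arm. Say whether early stops count as durations and, if so, include them.
- Simulate the planned Wilcoxon-Mann-Whitney test at 35 per arm, as was done for Hypothesis 1, and restate the power and the detectable difference.
- If the IQR of 50 to 100 h is kept, give its source and the arm it describes.

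The cost is a short simulation and one rewritten paragraph, with no change to data collection. The restated figure may be less favourable than 80% if patient-bolus use is high or differs between the arms.

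### The 80% power for duration ignores the plan's own serial gate; through the gate it is 59% to 79% at the plan's inputs, and the plan does not state it

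*Combined protocol and SAP*

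**What the plan says.** The Statistics section names two primary end points, average pain score on postoperative day 1 and duration of treatment, and states: "This study will be powered for two primary end points". It tests them in series: "Hypothesis 2 will not be formally tested unless the conclusion of Hypothesis 1 is at least" noninferiority.

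The Sample size estimate section gives one power figure for each end point.

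- **Pain (Hypothesis 1):** "Out of the 1000 trials, 792 (79.2%) correctly resulted in a conclusion of non-inferiority". This is with 35 per group, and the plan summarises the probability as "about 80% when the groups follow exactly equivalent distributions".
- **Duration (Hypothesis 2):** once noninferiority is concluded, "the investigators will test for a difference in overall duration of administration again using the Wilcoxon-Mann-Whitney test". For its power the plan says: "Power is approximated by a two-sample t-test calculation". With an SD of 37 hours and a two-sided 5% level, "the investigators expect that a sample size of n=35 provides 80% power to detect a mean group difference of 25 hours".

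The two figures are never combined. No power is given for duration through the serial procedure, or for both end points together.

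**The concern.** A formal success on duration needs two events in the same trial: pain is declared noninferior, and the duration test is significant. The t-test calculation covers only the second. Since the first is expected to fail in about one trial in five even when pain is identical in the two groups, the chance of both must in general be lower than the 80% stated.

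Longer duration is one of the two claims the trial is built to make. A reader who takes the 80% at face value will expect the claim to go unproven, when the 25-hour difference is real, in about one trial in five. Under the serial rule that risk could be as high as 41% (1 − 0.588), and it is 37% (1 − 0.630) if the two tests are independent.

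**Working it through.** **Inputs, all from the Statistics and Sample size estimate sections:** 35 per group; duration difference 25 h; SD 37 h; two-sided alpha 0.05; probability of passing the gate 792/1000 = 0.792 with identical pain distributions; duration tested only after the gate is passed.

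**Step 1. Reproduce the plan's 80%.**

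- Standardised difference: 25/37 = 0.676.
- Noncentrality: 0.676 × √(35/2) = 2.827, with 68 degrees of freedom.
- Two-sided t-test power at 5%: 0.7957, or 79.6%. The normal approximation gives 80.7%.

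The stated figure reproduces as stand-alone power, with no allowance for the gate.

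**Step 2. Bound the power through the gate.** Let p1 = 0.792 (gate passed) and p2 = 0.7957 (duration test significant). For any dependence between the two events, the probability of both lies between max(0, p1 + p2 − 1) and min(p1, p2).

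- Lower bound: 0.792 + 0.7957 − 1 = 0.588.
- Upper bound: min(0.792, 0.7957) = 0.792.
- Independence: 0.792 × 0.7957 = 0.630.

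Using the rounded 80% instead gives 59.2%, 79.2% and 63.4%. The last is also the unconditional power if the 80% is read as conditional on passing the gate (0.792 × 0.80).

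**Step 3. Allow for simulation error.** The Wilson 95% interval for 792/1000 is 0.766 to 0.816. The bounds widen to 0.766 + 0.7957 − 1 = 0.562 and min(0.816, 0.7957) = 0.796, so about 56% to 80%. The independence case becomes 61% to 65%.

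**Step 4. Between the bounds.** The documents give no correlation between the end points. As an illustration, a Gaussian copula with p1 = 0.792 and p2 = 0.80 gives 60.1% at a latent correlation of −0.5, 68.2% at +0.5 and 74.5% at +0.9.

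**Step 5. Other duration differences.** These are my assumptions, with SD 37 h, 35 per group and identical pain.

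| True difference | Stand-alone power | Bounds through the gate | Independence |
|---|---|---|---|
| 20 h | 60.6% | 39.8% to 60.6% | 48.0% |
| 25 h (plan) | 79.6% | 58.8% to 79.2% | 63.0% |
| 30 h | 91.7% | 70.9% to 79.2% | 72.6% |
| 35 h | 97.4% | 76.6% to 79.2% | 77.1% |

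A larger difference raises the lower bound. The upper bound cannot exceed the gate's own 79.2% (81.6% at the top of the Wilson interval).

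**Step 6. The planned test.** The bounds use the plan's t-test approximation. For the Wilcoxon-Mann-Whitney test actually planned, and assuming normal data, a simulation of 20,000 trials gives stand-alone power of about 77.6%. The bounds become about 57% to 78%, with 61% under independence.

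**The case against.** The best defence is that nothing was miscalculated. The 80% reproduces, the plan sets out the gate directly before the duration power, and the 79.2% stands just before that. A careful reader can take the 80% as the power of the second step once it is reached, and quoting about 80% for each end point is a common meaning of powering for both. It stands that the t-test arithmetic is right. But the plan does not say that the figure is conditional, and on that reading the unconditional power is still about 63% and still not given.

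A second line is that the range is built from extremes. Patient-controlled boluses draw on the same reservoir whose exhaustion ends the duration measure. Trials in which the bolus group happens to have more pain may therefore also show a shorter duration. That would be positive dependence and would put the power at or above the independence value. This is plausible, but it is an inference, and the documents give no correlation. Even a latent correlation of +0.9 reaches only about 75%.

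Third, 25 h is a difference to detect, not a forecast. Taken without any patient boluses, the stated pump settings empty 500 mL in about 83 h (500/6) and 125 h (500/4), a gap of about 42 h. Stand-alone power would then be 99.6% and the gated range 78.8% to 79.2%. Patient boluses would shrink that gap, so this is an illustration only. It shows that the shortfall can be small if the effect is large, but the cap at 79.2% remains.

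Finally, the 0.792 cannot be checked, because the discrete pain distribution is not given, and it applies only when pain is exactly equal. If boluses give better pain control the gate is passed more often; if slightly worse, less often. This limits how precisely the range should be read. It does not supply the missing figure.

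**Conclusion.** The concern holds. The 80% is the stand-alone power of a t-test for duration, and the serial procedure does not deliver it at the plan's inputs. Power for duration through the gate is 58.8% to 79.2% under any dependence (about 56% to 80% with simulation error) and 63.0% if the tests are independent.

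These figures rest on the plan's own 25 h, 37 h, 35 per group and 79.2%, on identical pain in the two groups, and on the plan's t-test approximation. Using the planned Wilcoxon-Mann-Whitney test with normal data lowers the range slightly. The serial procedure itself is not in question, nor is its control of type I error. The fault is that a trial described as powered for two primary end points gives, for the second, a power that leaves out its own testing rule. This should be corrected.

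**What to change.** In the Sample size estimate section, label the 80% as stand-alone power for duration. Next to it, state the power for Hypothesis 2 through the gate: 59% to 79% at 25 h with identical pain (about 56% to 80% with simulation error), with 63% as the independence case, and say that these use the t-test approximation.

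Preferably, extend the existing simulation to generate pain and duration jointly, apply the planned Wilcoxon-Mann-Whitney tests in sequence, and report the power over a range of dependence, true pain difference and duration difference.

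The cost is one relabelled figure, one added figure and a short extension of a simulation the investigators already have. Sample size, tests and alpha do not change. The only drawback is a less favourable stated power.
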